#### 6.3 Early withdrawal of subjects

Patients have the right to withdraw from the trial at any time and without giving any reason. If a patient withdraws from the trial, any and all information gathered prior to the withdrawal will be included in the analysis, though no further data collection will occur. If a patient does not attend planned follow-up appointments then two more attempts will be made to contact the patient regarding the study. If still no contact can be made then the patient is deemed lost to follow-up and any collected study data will be retained. Appendix 2, INTERVENTION DEVIATION AND LEG ULCER INFECTION, covers study withdrawals in more detail.

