#### 7.2 Safety definitions

Adverse Event (AE)	Any untoward medical occurrence in a patient or other clinical investigation participant taking part in a trial of a medical device, which does not necessarily have to have a causal relationship with the device under investigation.		
	An AE can therefore be any unfavourable and unintended sign		
	(including an abnormal laboratory finding), symptom or disease		
	temporally associated with the use of the device, whether or not		
	considered related to the device.		
Serious Adverse Event	A serious adverse event is any untoward medical occurrence that:		
	- results in death		
	- is life-threatening		
	
 
requires inpatient hospitalisation or prolongation of existing hospitalisation
 
		
	
 
results in persistent or significant disability/incapacity
 
consists of a congenital anomaly or birth defect.
 
		
	Other 'important medical events' may also be considered serious if they		
	jeopardise the participant or require an intervention to prevent one of		
	the above consequences.		
	NOTE: The term "life-threatening" in the definition of "serious" refers to		
	an event in which the participant was at risk of death at the time of the		
	event; it does not refer to an event which hypothetically might have		
	caused death if it were more severe.		

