#### 7.3 **Procedures for recording adverse events**

All SAEs need to be reported to the sponsor/host Trust R&D within one working day of the investigator team becoming aware of them.

The relationship of each adverse event to the trial must be determined by a medically qualified individual according to the following definitions:

- **Related**: The adverse event follows a reasonable temporal sequence from intervention. It cannot reasonably be attributed to any other cause.
- **Not Related**: The adverse event is probably produced by the participant's clinical state or by other modes of therapy administered to the participant.

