#### APPENDIX 2. INTERVENTION DEVIATION AND LEG ULCER INFECTION

There may be incidences where a participant may either:

- Develop a reaction to the allocated dressing/bandage
- Becomes completely non-compliant (possibly due to bandaging being uncomfortable, or eg hospital admission)
- Improve to such an extent that compression bandaging is no longer indicated.

In such instances the patient and/or clinician can opt to stop or pause treatment with the bandage in question. If this occurs, this needs to be recorded (date and reason), and the decision can then be made to either:

- Discontinuation due to improvement in symptoms (including wound healed). Participant will still continue to be assessed as per planned dates and timepoints.
- Change over to an alternative compression bandage that is not the originally allocated type. This is allowed but only if there are clinical indications to do so or at patient request if they cannot tolerate the allocated bandage type. Patient can later in trial period be transferred back to original allocated bandage type if required.
- Pausing or discontinuation of compression bandaging when not clinically indicated. Even if leg ulcer persists and patient no longer wears compression bandage, they can still continue in the trial if they wish. Outcome measures will continue to be recorded as per planned dates and timepoints.
- Pause of compression therapy due to adverse event. Patient can remain in trial provided they are capable to continue with follow-up schedule and completion of outcome measures. If not possible, see next point regarding 'Withdraw patient from study'.
- Withdraw patient from study.
  - At the request of the patient
  - For clinical reasons, eg if the leg has deteriorated to such an extent that emergency surgical or medical intervention is required which means return to use of compression bandage in reasonable time frame is not feasible. In this case, this needs to be reported as a (Serious) Adverse Event if discontinuation is due to deterioration of the index wound or index leg only.

When overall trial participation for a patient is finished early, the participant will still be asked to complete the relevant questionnaires (provided they have capacity to do so):

- Week 6 VEINES QoL questionnaire (if patient withdrawal before week 6)
- Week 12 VEINES QoL questionnaire (if patient withdrawal > week 6 and < week 12)

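### Appendix 2 ties (S)AE reporting at clinical withdrawal to the index wound or leg, while 7.2 and 7.3 require every SAE to be reported; the passages need reconciling

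*Protocol*

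**What the plan says.** Three places in the protocol bear on this.

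- **Sections 7.2 and 7.3.** The definition opens with "A serious adverse event is any untoward medical occurrence that" and then lists seriousness criteria, one being that the event "requires inpatient hospitalisation or prolongation of existing hospitalisation". An adverse event is described as one "which does not necessarily have to have a causal relationship with the device under investigation". The reporting rule is unconditional: "All SAEs need to be reported to the sponsor/host Trust R&D within one working day of the investigator team becoming aware of them".
- **Section 6.3.** This refers the reader to Appendix 2, which it says "covers study withdrawals in more detail".
- **Appendix 2.** One of the listed options is withdrawal from the study, either at the participant's request or for clinical reasons. The second is introduced as "For clinical reasons, eg if the leg has deteriorated to such an extent that emergency surgical or medical intervention is required". The item then asks, in this case, for an AE or SAE report "if discontinuation is due to deterioration of the index wound or index leg only".

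**The concern.** Section 7 and Appendix 2 appear to apply different tests to the same event. Section 7 asks whether the event is serious. Appendix 2 asks whether the discontinuation was due to the index wound or index leg. A serious event elsewhere in the body passes the first test and fails the second.

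At stake is the completeness of the safety record. The appendix is where the protocol sends staff for detail when a participant leaves, so a narrower condition there could be taken as the operative one. Section 9 says that no trial steering committee will be convened and that conduct is monitored by the in-house research team, so a missed report has few independent chances of being picked up.

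**Working it through.** No figure in the protocol depends on this and no arithmetic applies. The check is a comparison of the passages.

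**1. Scope of the section 7 rule.** Under 7.2 an event is serious if it meets a seriousness criterion. Body site plays no part, and an adverse event needs no causal link to the device. Section 7.3 then covers all serious events. Relatedness is assessed by a medically qualified individual, but it is not a condition for reporting.

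**2. Scope of the Appendix 2 rule.** The reporting instruction is conditional on the cause of discontinuation. Leg deterioration needing emergency intervention is given as an example of a clinical reason, not as the only one.

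**3. Which events reach the withdrawal item.** The option just before it in Appendix 2 covers pausing compression because of an adverse event, with no restriction to the leg. A participant who then cannot keep up follow-up and outcome measures is directed to the withdrawal item. Events unrelated to the leg therefore reach it by the appendix's own routing.

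**4. Test cases.** Each participant is withdrawn for clinical reasons.

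| Event leading to withdrawal | Sections 7.2 and 7.3 | Appendix 2, plain reading |
|---|---|---|
| Emergency admission, index leg deteriorated | SAE, reportable | Reportable |
| Emergency admission, other leg | SAE, reportable | Condition not met |
| Emergency admission, systemic event | SAE, reportable | Condition not met |
| Index leg deteriorated, no seriousness criterion met | AE, recorded (7.1) | Reportable as an AE |

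The second and third rows show the conflict. The fourth shows that the appendix also does something useful: it sets an explicit trigger for reporting index-leg deterioration that leads to withdrawal, even when it is not serious. A correction should not lose that.

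**5. Is there a bridging statement?** Appendix 2 contains no reference to 7.2 or 7.3, and nothing there says that other serious events leading to withdrawal remain reportable.

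**The case against.** The strongest reply is that the passages can be read together without conflict.

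- The words 'in this case' may refer back only to the example of a deteriorated leg. The restriction would then separate the index leg from the other leg, and a systemic event would fall outside the sentence and stay under 7.3.
- The sentence may only classify the withdrawal, saying when the discontinuation is itself an adverse event. It nowhere exempts another serious event, and 7.3 is unconditional.
- Section 6.3 refers to Appendix 2 for withdrawals, not for safety reporting.
- The event would leave some trace in any case. Appendix 2 asks for the date and reason when treatment is stopped or paused, and section 8.3 plans to report reasons for discontinuation.

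Much of this stands. Both readings are available, so it is not established that the authors meant to exempt anything or that staff would leave such events unreported. But neither reading is written down, and the first still leaves an admission for the other leg in doubt. A reason for discontinuation is also not the same as an SAE report within one working day.

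Two stronger inferences are tempting, and the documents do not support either. A reader might infer that serious events concentrate among clinical withdrawals; the protocol gives no data on this. A reader might also infer that reports would be lost unevenly between arms, because section 6.1.1 says participants cannot be blinded; but the Appendix 2 wording is the same for both arms and nothing in the protocol shows a differential effect.

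**Conclusion.** The point holds as a wording conflict in safety reporting. On a plain reading, Appendix 2 sets a narrower condition than 7.2 and 7.3 for the same event, and staff could fail to report a serious event outside the index leg that leads to withdrawal. This assumes that some staff would treat the appendix as the working instruction at withdrawal, which is plausible but not shown.

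The size cannot be computed. The only related figure is the 10% attrition allowance in section 6.1, which on 92 participants is 0.10 × 92 = 9.2, or about 9 people. That is a planning figure for withdrawals in general. It does not say how many would leave for clinical reasons, still less for reasons outside the index leg, and it should not be read as an estimate of missed reports.

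The sample size, the primary outcome and the primary analysis are unaffected. The matter is minor but worth correcting.

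**What to change.** Reconcile Appendix 2 with section 7 in the withdrawal item:

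1. Delete the word 'only'.
2. Add a sentence such as: any event leading to withdrawal, whatever its site or cause, is assessed against section 7.2 and, if serious, reported under section 7.3.
3. Keep the existing requirement that deterioration of the index wound or index leg leading to withdrawal is reported as an AE or SAE.

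Step 2 does most of the work, because deleting one word leaves the condition on cause in place. Step 3 matters because a rule that mentioned serious events alone would drop the present trigger for non-serious index-leg deterioration.

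The cost is about one sentence in an appendix and possibly a few more SAE forms. Treatment, visits and analyses do not change.

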#### Infection and use of antibiotics during trial

Patients do not have to withdraw from the study if infection occurs, as long as clinically there is a reason to continue with compression bandaging and it is deemed safe to do so. This applies for both oral and intravenous antibiotics use. If a treating clinician determines that compression bandaging should stop then this will be classed as an intervention deviation – see above.

## **APPENDIX 3 – CUMBRIA WOUND FORMULARY (2019)**

Retention Bandages	Mollelast / Actiwrap (finger & Toe) K-Band K-Lite
Padding	Flexiban (to use with Actico) Profore #1, (Cellona-Lymphoedema)
Tubular Bandage	Comfi-fast Comfi-fast Garments Comfigrip
Full Compression Bandages – Short Stretch	Actico
Multi-layer Compression Bandages	Coban 2, Coban 2 Lite
Compression Hosiery Applicator	Actiglide
Waterproof dressing protection	Limbo Sealtight
Dressing Packs	Polyfield Patient Pack Dressit
Skin Protection	Cavilon Cream Cavilon no-sting barrier Film Proshield Plus Skin Protectant
Compression Hosiery	Jobst Elvarex Custom Fit, Jobst Elvarex Soft Custom Fit, Sigvaris Optiform Hold Custom Fit, Sigvaris Optiform Flex Custom Fit, Haddenham (Veni, Star Cotton, microfine Toe caps)Juzo Soft, Medi, Mediven plus, Mediven Elegance, Jobst for Men, Ambition and Explore, Juzo, BSN
Protease Modulator	Urgostart Plus
Leg Wraps & Liners	Haddenham Easywrap Strong & Light, Jobst, BSN, Farrow wrap (Classic, lite, strong, 4000) Jobst Farrow Hybrid liner, Sigvaris Transition liner, Sigvaris Complete Liner, Juzo adjustable

## APPENDIX 4. STUDY PARTICIPANT FLOWCHART (BASED ON COHORT)
